7.2 Clinical Experience

E2027 is a new chemical entity. E2027 has been evaluated in 5 completed studies (E2027-A001-001[Study 001], E2027-A001-002 [Study 002], E2027-A001-003 [Study 003], E2027-A001-005 [Study 005], and E2027-G000-201 [Study 201]). In the completed Phase 1 studies, 176 subjects received at least 1 dose of E2027 (120 subjects administered single E2027 doses from 10 to 1200 mg in Study 001, Study 003, and Study 005, and 56 subjects administered multiple doses of E2027 from 5 to 400 mg once daily [QD] for up to 6 weeks in Study 002). In the completed Phase 2 study (Study 201), there were 200 subjects with DLB randomized in a 1:1 ratio to receive 50 mg of E2027 or placebo administered QD.

In the Phase 1 studies, E2027 was found to be well-tolerated at doses up to 400 mg QD for 14 days. Doses of E2027 at 50 mg QD or higher resulted in mean cerebrospinal fluid (CSF) cGMP elevation by approximately 200% from baseline at steady state, which was maintained after 6 weeks of treatment. This implied that >80% of subjects had at least 150% CSF cGMP elevation from baseline at a dose of E2027 50 mg QD.

Detailed description of clinical experience with E2027, including pharmacokinetic (PK), pharmacodynamic (PD), metabolism, and safety in Phase 1 studies, is provided in the E2027 Global Investigator's Brochure.

Study 201 was a Phase 2 proof of concept study. It was a randomized, double-blind, placebo-controlled study to determine the efficacy of a dose of E2027 (50 mg QD) compared to placebo in subjects with DLB. The key efficacy endpoints were Montreal Cognitive Assessment (MoCA), Clinician's Interview Based Impression of Change Plus Caregiver Input (CIBIC-Plus), Neuropsychiatric Inventory (NPI-12), and Cognitive Fluctuation Inventory (CFI). Details of the study design are provided in the E2027 Global Investigator's Brochure.

In Study 201, there were 99 subjects with mild to moderate DLB treated with E2027 50 mg QD and 97 subjects treated with placebo for up to 12 weeks. E2027 was well-tolerated. Most cases of treatment-emergent adverse events (TEAEs) were mild or moderate in

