based on the limited data of the correlation between CSF cGMP percentage change from baseline and change in efficacy endpoints, it was found that subjects with 190% to 200% increase from baseline in CSF cGMP showed improvement in MoCA and CIBIC-Plus, whereas subjects with <170% increase from baseline in CSF cGMP showed no improvement or worsening in these efficacy endpoints. Thus, it is considered that in subjects without amyloid copathology, if their CSF cGMP elevation is >30% higher than in subjects with amyloid copathology, this may be associated with clinically significant differences in efficacy as suggested by the subgroup results in Study 201. The absolute concentrations of CSF cGMP attained after treatment on E2027 between subjects with and without amyloid copathology will also be investigated for potential contribution to the difference in efficacy.

Pharmacogenomic blood samples will be collected to explore if genotypes associated with development or progression of DLB or deposition of amyloid copathology affect the CSF cGMP response to E2027.

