9.5.1.3.1 PHARMACOKINETIC ASSESSMENTS

Blood samples will be collected for the determination of plasma E2027 concentrations for PK analysis. Two blood samples for PK will be drawn at Weeks 6, 9, and 12: At predose (within 30 minutes before dosing) and 1 to 4 hours postdose. At these visits, subjects or their caregivers or informants will be instructed not to take their study drug at home on the day the blood samples for PK are collected. Instead, subjects will take their study drug at the clinic

after the predose blood draw; then a postdose blood draw will be performed. In addition, subjects or their caregivers or informant will be instructed to record the time of study drug administration for the 2 days before these visits when self-administered at home and this information will be collected and recorded on the eCRFs.

CSF samples will be collected for the determination of CSF E2027 concentrations at Week 9. At this visit, a predose blood sample for PK will be taken first, followed by CSF sampling. Study drug will then be administered to the subjects. Another PK sample will be collected at 1 to 4 hours postdose.

Plasma concentrations of E2027 and its metabolite HP4 and CSF concentrations of E2027 will be measured using validated liquid chromatography with tandem mass spectrometry (LC-MS/MS) assay methods.

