9.7.1.2 Definitions of Analysis Sets

The Safety Analysis Set is the group of subjects who receive at least 1 dose of study drug and have at least 1 post baseline safety assessment.

The Full Analysis Set (FAS) is the group of subjects who receive at least 1 dose of study drug and have baseline and at least 1 post baseline MoCA measurement.

The PD Analysis Set is the group of subjects who have sufficient PD data to derive at least 1 PD parameter.

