2 LIST OF ABBREVIATIONS AND DEFINITIONS OF TERMS

Abbreviation	Term
AChEI	acetylcholinesterase inhibitor
AE	adverse event
ATC	anatomical therapeutic class
BMI	body mass index
BP	Blood pressure
C-CASA	Columbia Classification Algorithm for Suicide Assessment
CI	confidence interval
CIBIC-Plus	Clinician's Interview Based Impression of Change Plus Caregiver Input
CFI	Cognitive Fluctuation Inventory
CGIC	Clinician Global Impression of Change
cGMP	cyclic guanosine monophosphate
CRF	case report form
CSF cGMP	cerebrospinal fluid
CSR	clinical study report
C-SSRS	Columbia Suicide Severity Rating Scale
CV	coefficient of variation
DBP	Diastolic blood pressure
DLB	Dementia in Lewy Bodies
ED	Early Discontinuation
FAQ	Functional Assessments Questionnaire
FAS	full analysis set
LLT	lower level term
LS	least squares
MDS	Movement Disorders Society
MedDRA	Medical Dictionary for Regulatory Activities
MMSE	Mini-Mental State Examination
MoCA	Montreal Cognitive Assessment
NPI	Neuropsychiatric Inventory

Abbreviation	Term
NPI-D	Neuropsychiatric Inventory – Distress symptoms
PD	pharmacodynamic
PDD	Parkinson's Disease Dementia
PK	pharmacokinetic
PT	Preferred term
QTcB	corrected QT interval calculated using Bazett's formula
QTcF	corrected QT interval calculated using Fridericia's formula
RBD	REM sleep behavior disorder
SAE	serious adverse event
SAP	statistical analysis plan
SAPS-PD	Scale for Assessment of Positive Symptoms in Parkinson's Disease
SBP	Supine blood pressure
SE	standard error
SI	Système International
SOC	System organ class
TEAE	treatment-emergent adverse event
TEMAV	treatment-emergent markedly abnormal laboratory value
TLG	tables, listings, and graphs
UPDRS-III	Unified Parkinson's Disease Rating Scale Part III: Motor Examination
WAIS-IV DSC	Wechsler Adult Intelligence Scale-4th Edition Digit Symbol Coding
WHO	World Health Organization
WHO DD	World Health Organization Drug Dictionary

Table 1 Summary of Changes (Version 2)

Changes in Version 2	Rationale

5.2.1 Definitions of Analysis Sets
 
Addition to the definition of subjects being excluded from the PD Analysis Set, based on low drug compliance/PK concentrations at Week 9.
	
Subjects with low PK concentrations, and therefore low drug compliance at Week 9 had outlying cGMP percentage change from baseline values. This was not helpful in determining proof of concept and hence they are to be excluded from the PD Analysis Set, and kept in all other analysis sets.

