5.2 Study Subjects

5.2.1 Definitions of Analysis Sets

The Safety Analysis Set is the group of subjects who receive at least 1 dose of study drug and have at least 1 post baseline safety assessment.

The Full Analysis Set (FAS) is the group of subjects who receive at least 1 dose of study drug and have baseline and at least 1 post baseline MoCA measurement.

The PD Analysis Set is the group of subjects who have sufficient PD data to derive at least 1 PD parameter. Subjects who have low drug compliance based on their PK results will be excluded from the PD Analysis Set. Lack of drug around the Week 9 CSF will affect the results of the CSF cGMP, and hence distort the primary endpoint interpretation.

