5.5.2 Pharmacodynamic, Pharmacogenomic, and Other Biomarker Analyses

Pharmacodynamic Analyses

The PD Analysis Set will be used for the summaries and analyses of CSF and plasma PD biomarkers. The percentage change from baseline in CSF cGMP at 9 weeks of treatment will be analyzed to compare different subject subgroups (DLB without amyloid copathology vs DLB with amyloid copathology, and PDD without amyloid copathology vs PDD with amyloid copathology). Secondary comparisons will be: total (DLB+PDD) without amyloid vs with amyloid, DLB without amyloid vs PDD without amyloid, and DLB with amyloid vs PDD with amyloid.

Analyses, comparing the different subgroups, of the percentage change from baseline in CSF cGMP will be performed using an analysis of covariance, where baseline CSF cGMP will be included as a covariate. The least square (LS) means, LS mean subgroup differences and 95% CIs will be presented.

The change from baseline in CSF cGMP at 9 weeks of treatment will also be analyzed. Other CSF and plasma PD biomarkers (CSF amyloid, plasma p-tau181, CSF p-tau181, plasma neurogranin, plasma neurofilament, CSF neurogranin, CSF neurofilament, etc) may be analyzed similarly, if appropriate.

The CSF and plasma PD biomarkers (both percentage change and change from baseline at 9 weeks) will be summarized by subgroups, as defined in section 5.3.4.

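### The primary CSF cGMP analysis excludes subjects under a compliance rule that was added after their values were seen, has no cut-off, and has no companion analysis on the protocol-defined set

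*SAP*

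**What the plan says.** Protocol 9.7.1.2 defines the set by data availability alone: "The PD Analysis Set is the group of subjects who have sufficient PD data to derive at least 1 PD parameter". SAP 5.2.1 keeps that sentence and adds: "Subjects who have low drug compliance based on their PK results will be excluded from the PD Analysis Set". The reason given there is that absence of drug around the Week 9 lumbar puncture would affect CSF cGMP and distort the reading of the primary endpoint.

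SAP Table 1 (Summary of Changes, Version 2) describes the exclusion as "based on low drug compliance/PK concentrations at Week 9". Its rationale is that subjects with low concentrations "had outlying cGMP percentage change from baseline values. This was not helpful in determining proof of concept and hence they are to be excluded". It also says they stay in all other analysis sets. The table is cited here only as evidence of why the rule was added; the rule itself is current text.

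SAP 5.5.2 ties the primary analysis to this set: "The PD Analysis Set will be used for the summaries and analyses of CSF and plasma PD biomarkers". SAP Section 7 states that the planned analyses are unchanged.

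**The concern.** An exclusion written after the outcome has been seen can move the estimate, even when the motive is sound. Three things leave it unprotected.

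- **No operating definition.** Low is not given as a concentration, and nobody is named to decide. Protocol 9.5.1.3.1 says of Week 9: "At this visit, a predose blood sample for PK will be taken first, followed by CSF sampling". A postdose plasma sample follows. Predose plasma and CSF E2027 are both candidates, and the SAP does not choose.
- **No second result.** The SAP plans no CSF cGMP analysis on the protocol-defined set.
- **The change is not declared where a reader would look.** SAP Section 7 conflicts with SAP Table 1 and with the difference from the protocol definition. Protocol 9.7.5 requires SAP revisions to be described in the study report.

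The primary comparison is the cGMP rise without versus with amyloid copathology, on about 6 completers per subgroup. Protocol 7.3 says the results will guide which subgroups go forward to Phase 3. Protocol 9.2 says it may be associated with clinically significant differences in efficacy "if their CSF cGMP elevation is >30% higher than in subjects with amyloid copathology". As the SAP is written, two analysts could exclude different subjects and both comply.

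**Working it through.** **Is the rule defined elsewhere in the SAP?** The only numeric compliance bands are in SAP 5.2.6. They are capsule counts on the Safety Analysis Set and are not linked to this exclusion. SAP 5.3.5 (missing data, dropouts and outliers) has efficacy and safety subsections only, and 5.7 (other analyses) is marked not applicable. Neither a cut-off nor a sensitivity analysis for cGMP appears.

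**Inputs from the documents.** SD 60 percentage points and 6 completers per subgroup (Protocol 9.7.2, SAP 4). Difference of interest 30 points (Protocol 9.2). Mean cGMP rise 168% in the four Study 201 subjects with CSF, and in Phase 1 "cGMP elevation by approximately 200% from baseline at steady state" (Protocol 7.2).

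**Assumptions.** A mean rise of 150% is used as a lower value; the protocol gives 150% as a level thought necessary for efficacy, not as a mean. One subject in one subgroup is low-drug and has a fraction f of the full response (0 or 0.5). Outcomes are normal and unadjusted.

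**The plan's own figures.** SE = 60 × √(1/6 + 1/6) = 34.6. P(observed difference ≥ 30) = 1 − Φ((30 − D)/34.6). For true D = 100, 60 and 10 this gives 97.8%, 80.7% and 28.2%, exactly as stated. For D = 0 it gives 19.3%.

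**Shift in a subgroup mean from one subject.** Shift = m(1 − f)/6, where m is the mean rise.

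- f = 0: 150/6 = 25.0; 168/6 = 28.0; 200/6 = 33.3.
- f = 0.5: 12.5, 14.0, 16.7.

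**Probability of observing ≥ 30 when dosed subjects do not differ.** If the subject is dropped (5 v 6), SE = 60 × √(1/5 + 1/6) = 36.3 and P = 1 − Φ(30/36.3) = 20.4%. If kept, SE stays 34.6. The expected difference (without minus with amyloid) is then +shift when the subject is in the with-amyloid subgroup and −shift when in the without-amyloid subgroup.

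| m | f | Kept, with amyloid | Kept, without amyloid |
|---|---|---|---|
| 150 | 0 | 44.3% | 5.6% |
| 168 | 0 | 47.7% | 4.7% |
| 200 | 0 | 53.8% | 3.4% |
| 150 | 0.5 | 30.7% | 11.0% |
| 168 | 0.5 | 32.2% | 10.2% |
| 200 | 0.5 | 35.0% | 8.9% |

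**With baseline adjustment.** Simulating the planned ANCOVA (40,000 trials per setting, m = 150 and 200, assumed correlation of baseline with percentage change 0 or −0.5) gives the same picture. Mean shifts are 12 to 17 points (f = 0.5) and 25 to 34 points (f = 0). P is 18% to 22% if dropped. If kept with f = 0, it is 44% to 54% (with amyloid) or 3% to 7% (without amyloid).

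**A limiting case of outcome-led exclusion.** Suppose all 12 subjects are on drug with no true difference, and the lowest value in the without-amyloid subgroup is removed simply for being low. P(≥ 30) then rises from 19% to 34% (400,000 simulations). This is not the SAP rule. It shows what a cut-off influenced by cGMP values could do.

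**The case against.** The strongest reply is that excluding undosed subjects is right for a pharmacodynamic question, and the figures support it. Dropping a truly undosed subject gives 20%, close to the 19% with everyone on drug, while keeping that subject is what distorts the result. That stands, and it justifies an exposure-restricted analysis. It does not justify leaving the cut-off open or making this the only analysis.

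Other points stand in part:

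- Nothing shows that predose plasma and CSF would classify anyone differently; they are taken consecutively before dosing. The ambiguity is in the text, and its practical effect is unknown.
- A flagging rule or extra table may exist in the dataset specifications (SAP Section 9), the table shells (SAP Section 11) or the separate PK/PD plan. None was available, so the gap is established for the SAP text only.
- Concentrations are still listed and summarized on the Safety Analysis Set (SAP 5.5.1), so the excluded subjects' exposure stays visible. Their cGMP result still drops out of the primary analysis.
- The change is disclosed in SAP Table 1, so correcting Section 7 is housekeeping. Disclosure supplies neither a cut-off nor a second estimate.
- The study is open-label and estimation only, and Protocol 9.7.2 expects no statistical significance. That makes the point estimate the basis for what follows, so its dependence on the exclusion should be visible.

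Protocol 9.7 requires the SAP to be final before database lock. The documents do not date Version 2 against lock, and nothing here implies that it came after.

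**Conclusion.** The concern holds. The current SAP departs from the protocol's definition of the PD Analysis Set through an exclusion prompted by observed primary-endpoint values, gives no numeric criterion or deciding sample, and plans the primary analysis on that set alone.

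Under the stated assumptions, one low-drug subject is worth 25 to 33 points in a subgroup mean at zero response and 12.5 to 17 at half response, against a 30-point difference of interest. With no true difference among dosed subjects, the chance of seeing 30 or more is about 20% with that subject excluded. With a zero-response subject kept, it is 44% to 54% or 3% to 6%, depending on the subgroup. These figures show how much one classification matters; they do not show that the sponsor's exclusion biased the result. The actual number, subgroups and effect of the exclusions cannot be determined from the documents.

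The replacement rule in Protocol 9.5.5 counts subjects who complete 9 weeks and the second CSF sample. Exclusion from this set does not trigger it, so an analysed subgroup can fall below 6. This should be fixed before the primary result is reported.

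**What to change.** 1. Present the CSF cGMP summaries and ANCOVA side by side on the PD Analysis Set as defined in Protocol 9.7.1.2 and on the exposure-restricted set.
2. Define the restricted set by a named Week 9 sample (predose plasma, CSF E2027, or a stated combination) and a numeric cut-off set from earlier-study PK data. Have the cut-off set and applied without reference to cGMP. Because cGMP values have already been seen, this cannot be fully outcome-blind, which is why the first item matters most.
3. List each excluded subject with subgroup, Week 9 concentrations and cGMP change.
4. Amend SAP Section 7 to record the departure from the protocol-defined set and that it followed sight of cGMP values, and carry this into the study report as Protocol 9.7.5 requires.

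The cost is SAP wording, one further ANCOVA table, one listing, and retrieval of existing PK data for the cut-off. No new data are collected. The drawback is that two results may differ and will need explaining.

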5.2.2 Subject Disposition

The number of subjects screened, the number (percent) of subjects who failed screening, and the reasons for screen failure will be summarized, based on data reported on the Screening Disposition electronic case report form (eCRF). The distribution of the number of subjects enrolled by each site will be summarized by subgroup and overall.

Study Completion, defined as completing 12 weeks of study and the follow up visit: The number (percent) of treated subjects who completed the study and who discontinued from the study will be summarized according to the primary reason for discontinuation and secondary reason(s) for discontinuation, based on data reported on the Subject Disposition (Study Phase) eCRF. The number (percent) will be presented by subgroup and total for all subjects.

Completion of Study Treatment, defined as completing 12 weeks of study: The number (percent) of treated subjects who completed study drug and who discontinued from study drug will be summarized according to the primary reason for discontinuation and also according to secondary reason(s) for discontinuation, based on data reported on Early Discontinuation from Study Drug eCRF. The number (percent) will be presented by subgroup and total for all subjects. Subjects who discontinued study treatment but were followed up for efficacy assessments after treatment discontinuation will also be summarized.

5.2.3 Protocol Deviations

A summary table and listing will be produced with critical protocol deviations.

5.2.4 Demographic and Other Baseline Characteristics

Demographic and other baseline characteristics for the Safety Analysis Set and FAS will be summarized for each subgroup and overall using descriptive statistics. Continuous demographic and baseline variables include age, age at diagnosis, age at onset, years since onset of symptoms, NPI hallucinations FxS score, body weight, height, disease duration, baseline MDS-UPDRS part III score, SFQ Score, Modified Hachinski Ischemic Scale, average time per day for caregiver to spend with patient, and average days per week for caregiver to spend with patient. Categorical variables include sex, age group (less than 65 years, age greater than or equal to 65 years), age group at diagnosis, age group at onset, race, ethnicity, treatment with AChEIs (no or yes), Columbia Classification Algorithm for Suicide Assessment (C-CASA), C-SSRS not completed (missing), Hoehn & Yahr stage and subgroups (0, I, II vs III, IV, V), NPI hallucinations FxS score subgroups (<median, \geq median), relationship of caregiver to patient, caregiver reside with the patient (yes or no), caregiver's time per week to spend with subject (<median, \geq median), have each clinical DLB core feature (hallucination, fluctuation, parkinsonism, rapid eye movement sleep behavior disorder [RBD]) (yes or no), and have 2 or more core clinical DLB feature or have only 1 clinical feature (Appendix 1 of protocol: Diagnostic Criteria for Probable Dementia With Lewy Bodies (DLB)), have each clinical supportive feature of DLB, have each indicative biomarker of DLB, Parkinsonian Symptoms (yes or no), bradykinesia under PDD (Yes, No), at least one of the other clinical features of PDD (muscular rigidity, 4-6 Hz rest tremor, postural instability) (yes or no), PDD symptoms severe enough to impair work/activities (yes or no).

Biomarker data will be summarized under the PD Analysis Set for each subgroup and overall using descriptive statistics. Continuous variables include CSF cGMP, plasma A β 42, plasma A β 40, CSF A β 42, CSF A β 40, CSF A β 42/40 ratio, plasma p-tau181, plasma p-tau181/A β (1-42), CSF p-tau181, CSF p-tau181/A β (1-42), plasma neurogranin, plasma neurofilament light (NfL), plasma GFAP, CSF neurogranin, CSF neurofilament light, and any other appropriate biomarkers. Categorical variables include A β 42/40 ratio (<0.092, \geq 0.092), CSF A β 42/40 ratio (<0.0571, \geq 0.0571) [Ref 1], ApoE4 (positive, negative), ApoE categories, plasma p-tau181 (<2.2, \geq 2.2 μ g/mL), plasma p-tau181/A β (1-42) ratio (<0.043, \geq 0.043), CSF total tau (<400, \geq 400 μ g/mL), CSF ptau-181 (<52.8, \geq 52.8 μ g/mL), CSF p-tau181/A β (1-42) ratio (<0.083, \geq 0.083), CSF total tau/A β (1-42) ratio (<0.637, \geq 0.637) and other groups of biomarkers as appropriate. If numbers allow, combinations as follows will be calculated:

a) Based on plasma A β 42/40 and apolipoprotein E4 (ApoE4):

- A β 42/40 <0.092 and ApoE4 positive,
- A β 42/40 <0.092 and ApoE4 negative,
- A β 42/40 \geq 0.092 and ApoE4 negative,
- A β 42/40 \geq 0.092 and ApoE4 positive,

b) Based on CSF A β 42/40 and ApoE4

- CSF A β 42/40 <0.0571 and ApoE4 positive,

- CSF A β 42/40 <0.0571 and ApoE4 negative,
- CSF A β 42/40 \geq 0.0571 and ApoE4 negative,
- CSF A β 42/40 \geq 0.0571 and ApoE4 positive.

Clinical efficacy data will be summarized under the FAS for each subgroup and overall using descriptive statistics. Continuous variables include MoCA total score, NPI total score, NPI-4 score, NPI-10 score, NPI-D score, NPI subscores, MMSE total score, CFI score, WAIS-IV DSC, SAPS-PD and FAQ. Categorical variables include CIBIC Plus and subitems, and MMSE total score subgroup (14-19, 20-26).

Where Screening values are collected, these may be summarized also.

Where the date of diagnosis only contains the year of diagnosis, the age of diagnosis will use the year of diagnosis – year of birth.

MEDICAL HISTORY

The medical history verbatim descriptions (investigator terms from the CRF) will be classified into standardized medical terminology using the Medical Dictionary for Regulatory Activities (MedDRA). Medical history will be coded to the MedDRA (Version 23.1 or higher) lower level term (LLT) closest to the verbatim term. The linked MedDRA preferred term (PT) and primary system organ class (SOC) will also be captured in the database.

The number (percent) of subjects will be presented by SOC and PT for each subgroup and total.

